- Having at least one claim for alternative indications; orthopedic procedures, VTE (includes DVT &PE) and the index NOAC prescription at the same time, or, the alternative indication for anticoagulant occurring within 3 months prior to index date in pre-period Having at least one claim with any of the following diagnoses or procedure codes in order to exclude patients with “transient” causes of Afib (3 months prior to index date in pre-period):
 - Cardiac surgery
 - Pericarditis
 - Myocarditis
- Having at least one medical claim with any of the following diagnoses or procedures codes in order to exclude patients with “valvular” Afib (pre-period):
 - Mitral stenosis
 - Mitral stenosis with insufficiency
 - Mitral valve stenosis and aortic valve stenosis
 - Mitral valve stenosis and aortic valve insufficiency
 - Diseases of other endocardial structures
 - Other and unspecified rheumatic heart diseases
 - Open heart valvuloplasty without replacement
 - Open and other replacement of unspecified heart valve
 - Open and other replacement of aortic valve

- Open and other replacement of mitral valve
- Open and other replacement of pulmonary valve
- Open and other replacement of tricuspid valve
- Heart valve replaced by transplant
- Heart valve replaced by a mechanical device/prosthesis
- Atrioventricular valve repair
- Aortic valve valvuloplasty
- Unlisted procedure, cardiac surgery
- Implantation of catheter-delivered prosthetic aortic heart valve; open thoracic approach
- Transthoracic cardiac exposure (e.g., sternotomy, thoracotomy, subxiphoid) for catheter-delivered aortic valve replacement; without cardiopulmonary bypass
- Transthoracic cardiac exposure (e.g., sternotomy, thoracotomy, subxiphoid) for catheter-delivered aortic valve replacement; with cardiopulmonary bypass
- Replacement, aortic valve, with cardiopulmonary bypass; with prosthetic valve other than homograft or stentless valve
- Valvuloplasty, mitral valve, with cardiopulmonary bypass
- Valvuloplasty, mitral valve, with cardiopulmonary bypass; with prosthetic ring
- Valvuloplasty, mitral valve, with cardiopulmonary bypass; radical reconstruction, with or without ring
- Replacement, mitral valve, with cardiopulmonary bypass
- Implantation of catheter-delivered prosthetic pulmonary valve, endovascular approach
- Replacement, pulmonary valve
- Valvectomy, tricuspid valve, with cardiopulmonary bypass
- Valvuloplasty, tricuspid valve; without ring insertion

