Myocarditis	391.2, 422.xx, 074.23, 398.0, 429.0, 032.82, 036.43, 093.82, 130.3	A36.81, A38.1, A39.52, A52.06, A54.83, B26.82, B33.22, B58.81, D86.85, I01.2, I09.0, I40.0, I40.1, I40.8, I41, I511.4, J10.82, J11.82
Pulmonary Embolism	415.1x	I26.01, I26.09, I26.90, I26.92, I26.99, I27.82
Valvular Afib		
Mitral stenosis	394.0x	I05.0, I05.1, I05.2, I05.8, I05.9, I34.2
Mitral stenosis with insufficiency	394.2	I34.0, I34.2, I34.8, I34.9
Mitral valve stenosis and aortic valve stenosis	396.0	I06.0, I35.0, Q23.0
Mitral valve stenosis and aortic valve insufficiency	396.1	I08.0, I06.1, I25.1, Q23.1, Q23.8, Q23.9

Diseases of other endocardial structures	397.x	I07.x, I09.89, I08.1, I08.2, I08.3, I08.8, I08.9
Other and unspecified rheumatic heart diseases	398.9x	I09.9, I09.81, I09.89
Heart valve replaced by transplant	V42.2	Z95.3, Z95.4
Heart valve replaced by a mechanical device/prosthesis	V43.3	Z95.2
Atrioventricular valve repair	V43.3	Z95.2
Aortic valve valvuloplasty/diseases of aortic valve	395.x	I06.x

Table 3. List of codes and descriptions to identify patients with exclusion procedures

Subject Exclusion Criteria:	ICD9 Procedure Codes	ICD10 Procedure Codes	CPT Codes
Valvular Afib Procedure/CPT codes			
Open heart valvuloplasty without replacement	35.1x	02QF0ZZ, 02QG0ZZ, 02QH0ZZ, 02QJ0ZZ, 027F04Z, 027F0DZ, 027F0ZZ, 02NF0ZZ, 02QF0ZZ, 027G04Z, 027G0DZ, 027G0ZZ, 02NG0ZZ, 02QG0ZZ, 027H04Z, 027H0DZ, 027H0ZZ, 02NH0ZZ, 02QH0ZZ, 027J04Z, 027J0DZ, 027J0ZZ, 02NJ0ZZ, 02QJ0ZZ	

Open And Other Replacement Of Heart Valve (This includes : Open and other replacement of unspecified heart valve, Open and other replacement of aortic valve, Open and other replacement of mitral valve , Open and other replacement of mitral valve , Open and other replacement of pulmonary valve, Open and other replacement of tricuspid valve.)	35.2x	02RF07Z, 02RF08Z, 02RF0JZ, 02RF0KZ, 02RF47Z, 02RF48Z, 02RF4JZ, 02RF4KZ, 02RG07Z, 02RG08Z, 02RG0JZ, 02RG0KZ, 02RG47Z, 02RG48Z, 02RG4JZ, 02RG4KZ, 02RH07Z, 02RH08Z, 02RH0JZ, 02RH0KZ, 02RH47Z, 02RH48Z, 02RH4JZ, 02RH4KZ, 02RJ07Z, 02RJ08Z, 02RJ0JZ, 02RJ0KZ, 02RJ47Z, 02RJ48Z, 02RJ4JZ, 02RJ4KZ, 02RF07Z, 02RF08Z, 02RF0KZ, 02RF47Z, 02RF48Z, 02RF4KZ, X2RF032, X2RF432, 02RF0JZ, 02RF4JZ, 02RG07Z, 02RG08Z, 02RG0KZ, 02RG37Z, 02RG38Z, 02RG3KZ, 02RG47Z, 02RG48Z, 02RG4KZ, 02RG0JZ, 02RG3JZ, 02RG4JZ, 02RH07Z, 02RH08Z, 02RH0KZ, 02RH47Z, 02RH48Z, 02RH4KZ, 02RH0JZ, 02RH4JZ, 02RJ07Z, 02RJ08Z, 02RJ0KZ, 02RJ47Z, 02RJ48Z, 02RJ4KZ, 02RJ0JZ, 02RJ4JZ	

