Closed Heart Valvotomy	35.0x	02NF3ZZ, 02NF4ZZ, 02NG3ZZ, 02NG4ZZ, 02NH3ZZ, 02NH4ZZ, 02NJ3ZZ, 02NJ4ZZ, 02NF3ZZ, 02NF4ZZ, 02NG3ZZ, 02NG4ZZ, 02NH3ZZ, 02NH4ZZ, 02NJ3ZZ, 02NJ4ZZ, 02RF37Z, 02RF38Z, 02RF3JZ, 02RF3KZ, X2RF332, 02RF37H, 02RF38H, 02RF3JH, 02RF3KH, 02RH37Z, 02RH38Z, 02RH3JZ, 02RH3KZ, 02RH37H, 02RH38H, 02RH3JH, 02RH3KH, 02RF37Z, 02RF38Z, 02RF3JZ, 02RF3KZ, 02RG37H, 02RG37Z, 02RG38H, 02RG38Z, 02RG3JH, 02RG3JZ, 02RG3KH, 02RG3KZ,	

		02RH37Z, 02RH38Z, 02RH3JZ, 02RH3KZ	
Unlisted procedure, cardiac surgery			33999
Implantation of catheter-delivered prosthetic aortic heart valve; open thoracic approach			0257T
Transthoracic cardiac exposure (e.g., sternotomy, thoracotomy, subxiphoid) for catheter-delivered aortic valve replacement; without cardiopulmonary bypass			0258T
Transthoracic cardiac exposure (e.g., sternotomy, thoracotomy, subxiphoid) for catheter-delivered aortic valve replacement; with cardiopulmonary bypass			0259T
Replacement, aortic valve, with cardiopulmonary bypass; with prosthetic valve other than homograft or			33405

stentless valve			
Valvuloplasty, mitral valve, with cardiopulmonary bypass			33425
Valvuloplasty, mitral valve, with cardiopulmonary bypass; with prosthetic ring			33426
Valvuloplasty, mitral valve, with cardiopulmonary bypass; radical reconstruction, with or without ring			33427
Replacement, mitral valve, with cardiopulmonary bypass			33430
Implantation of catheter-delivered prosthetic pulmonary valve, endovascular approach			0262T
Replacement, pulmonary valve			33475
Valvectomy, tricuspid valve, with cardiopulmonary bypass			33460
Valvuloplasty, tricuspid valve; without ring insertion			33463
Valvuloplasty, tricuspid valve; with ring insertion			33464
Replacement, tricuspid valve, with			33465

Proprietary confidential information © 2016 Boehringer Ingelheim International GmbH or one or more of its affiliated companies

cardiopulmonary bypass			
Description for CPT=33660-33665			33660 - 33665
Description for CPT=33400-33403			33400 - 33403
Orthopedic Procedures (Hip/Knee)			
Total/Partial Hip Replacement	81.52	0SRA009,0SRA00A,0SRA00Z, 0SRA019,0SRA01A,0SRA01Z, 0SRA039,0SRA03A,0SRA03Z, 0SRA07Z,0SRA0J9,0SRA0JA,0 SRA0JZ,0SRA0KZ,0SRE009,0 SRE00A,0SRE00Z,0SRE019,0S RE01A,0SRE01Z,0SRE039,0S RE03A,0SRE03Z,0SRE07Z,0S RE0J9,0SRE0JA,0SRE0JZ,0SR E0KZ,0SRR019,0SRR01A,0SR R01Z,0SRR039,0SRR03A,0SR R03Z,0SRR07Z,0SRR0J9,0SRR 0JA,0SRR0JZ,0SRR0KZ,0SRS 019,0SRS01A,0SRS01Z,0SRS0 39,0SRS03A,0SRS03Z,0SRS07 Z,0SRS0J9,0SRS0JA,0SRS0JZ	

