Cardiac Surgery	00.5x, 35.xx, 36.xx, 37.xx	0210083,0210088,0210089,021008C,021008F,021008W,0210093,0210098,0210099,021009C,021009F,021009W,02100A3,02100A8,02100A9,02100AC,02100AF,02100AW,02100J3,02100J8,02100J9,02100JC,02100JF,02100JW,02100K3,02100K8,02100K9,02100KC,02100KF,02100KW,02100Z3,02100Z8,02100Z9,02100ZC,02100ZF,0210344,02103D4,0210444,0210483,0210488,0210489,021048C,021048F,021048W,0210493,0210498,0210499,021049C,021049F,021049W,	
		02104A3,02104A8,02104A9,02104AC,02104AF,02104AW,02104D4,02104J3,02104J8,02104J9,02104JC,02104JF,02104JW,02104K3,02104K8,02104K9,02104KC,02104KF,02104KW,02104Z3,02104Z8,02104Z9,02104ZC,02104ZF,0211083,0211088,0211089,021108C,021108F,021108W,0211093,0211098,0211099,021109C,021109F,021109W,021	

	10A3,02110A8,02110A9,02110AC,02110AF,02110AW,02110J3,02110J8,02110J9,02110JC,02110JF,02110JW,02110K3,02110K8,02110K9,02110KC,02110KF,02110KW,02110Z3,02110Z8,02110Z9,02110ZC,02110ZF,0211344,	
	02113D4,0211444,0211483,0211488,0211489,021148C,021148F,021148W,0211493,0211498,0211499,021149C,021149F,021149W,02114A3,02114A8,02114A9,02114AC,02114AF,02114AW,02114D4,02114J3,02114J8,02114J9,02114JC,02114JF,02114JW,02114K3,02114K8,02114K9,02114KC,02114KF,02114KW,02114Z3,02114Z8,02114Z9,02114ZC,02114ZF,0212083,0212088,0212089,021208C,021208F,021208W,0212093,0212098,0212099,021209C,021209F,021209W,02120A3,02120A8,02120A9,02120AC,02120AF,02120AW,02120J3,02120J8,02120J9,02120JC,	
	02120JF,02120JW,02120K3,02120K8,02120K9,02120KC,02120KF,02120KW,02120Z3,02120Z8,02120Z9,02120ZC,02120ZF,0212344,02123D4,0212444,0212483,0212488,0212489,021248C,021248F,021248W,0212493,0212498,0212499,021249C,021249F,021249W,02124A3,02124A8,02124A9,02124AC,02124AF,02124AW,02124D4,02124J3,02124J8,02124J9,02124JC,02124JF,02124JW,02124K3,02124K8,02124K9,02124KC,02124KF,02124KW,02124Z3,02124Z8,02124Z9,02124ZC,02124ZF,0213083,0213088,0213089,021308C,021308F,021308W,0213093,0213	

		098,0213099,021309C,021309F, 021309W,02130A3,02130A8,02 130A9,02130AC,02130AF,0213 0AW,	
		02130J3,02130J8,02130J9,0213 0JC,02130JF,02130JW,02130K 3,02130K8,02130K9,02130KC, 02130KF,02130KW,02130Z3,0 2130Z8,02130Z9,02130ZC,021 30ZF,0213344,02133D4,021344 4, 0213483,0213488,0213489,021 348C,021348F,021348W,02134 93,0213498,0213499,021349C,0 21349F,021349W,02134A3,021 34A8,02134A9,02134AC,02134 AF,02134AW,02134D4,02134J 3,02134J8,02134J9,02134JC,02 134JF,02134JW,02134K3,0213 4K8,02134K9,02134KC,02134 KF,02134KW,02134Z3,02134Z 8,02134Z9,02134ZC,02134ZF,0 21608P,021608Q,021608R,0216 09P,	

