		02560ZZ,02563ZZ,02564ZZ,02570ZK,02570ZZ,02573ZK,02573ZZ,02574ZK,02574ZZ,02580ZZ,02583ZZ,02584ZZ,02590ZZ,02593ZZ,02594ZZ,025D0ZZ,025D3ZZ,025D4ZZ,025F0ZZ,025F3ZZ,025F4ZZ,025G0ZZ,025G3ZZ,025G4ZZ,025H0ZZ,025H3ZZ,025H4ZZ,025J0ZZ,025J3ZZ,025J4ZZ,025K0ZZ,025K3ZZ,025K4ZZ,025L0ZZ,025L3ZZ,025L4ZZ,025M0ZZ,025M3ZZ,025M4ZZ,025N0ZZ,025N3ZZ,025N4ZZ,0270046,027004Z,0270056,027005Z,0270066,027006Z,0270076,027007Z,02700D6,027	

		00DZ,02700E6,02700EZ,02700 F6,02700FZ,02700G6,	
		02700GZ,02700T6,02700TZ,02 700Z6,02700ZZ,0270346,02703 4Z,0270356,027035Z,0270366,0 27036Z,0270376,027037Z,0270 3D6,02703DZ,02703E6,02703E Z,02703F6,02703FZ,02703G6,0 2703GZ,02703T6,02703TZ,027 0446,027044Z,0270456,027045 Z,0270466,027046Z,0270476,02 7047Z,02704D6,02704DZ,0270 4E6,02704EZ,02704F6,02704F Z,02704G6,02704GZ,02704T6, 02704TZ,0271046,027104Z,027 1056,027105Z,0271066,027106 Z,0271076,027107Z,02710D6,0 2710DZ,02710E6,02710EZ,027 10F6,02710FZ,02710G6,02710 GZ,02710T6,02710TZ,02710Z6 ,02710ZZ,0271346,027134Z,	
		0271356,027135Z,0271366,027 136Z,0271376,027137Z,02713D 6,02713DZ,02713E6,02713EZ,0 2713F6,02713FZ,02713G6,0271 3GZ,02713T6,02713TZ,027144 6,027144Z,0271456,027145Z,02 71466,027146Z,0271476,02714 7Z,02714D6,02714DZ,02714E6 ,02714EZ,02714F6,02714FZ,02 714G6,02714GZ,02714T6,0271 4TZ,0272046,027204Z,0272056 ,027205Z,0272066,027206Z,027 2076,027207Z,02720D6,02720 DZ,02720E6,02720EZ,02720F6, 02720FZ,02720G6,02720GZ,02 720T6,02720TZ,02720Z6,02720 ZZ,	

		0272346,027234Z,0272356,027235Z,027236,027236Z,0272376,027237Z,02723D6,02723DZ,02723E6,02723EZ,02723F6,02723FZ,02723G6,02723GZ,02723T6,02723TZ,0272446,027244Z,0272456,027245Z,0272466,027246Z,0272476,027247Z,02724D6,02724DZ,02724E6,02724EZ,02724F6,02724FZ,02724G6,02724GZ,02724T6,02724TZ,0273046,027304Z,0273056,027305Z,0273066,027306Z,0273076,027307Z,02730D6,02730DZ,02730E6,02730EZ,02730F6,02730FZ,02730G6,02730GZ,02730T6,02730TZ,02730Z6,02730ZZ,0273346,027334Z,0273356,027335Z,0273366,027336Z,0273376,027337Z,02733D6,02733DZ,02733E6,02733EZ,02733F6,02733FZ,	
		02733G6,02733GZ,02733T6,02733TZ,0273446,027344Z,0273456,027345Z,0273466,027346Z,0273476,027347Z,02734D6,02734DZ,02734E6,02734EZ,02734F6,02734FZ,02734G6,02734GZ,02734T6,02734TZ,027F04Z,027F0DZ,027F0ZZ,027F34Z,027F3DZ,027F3ZZ,027F44Z,027F4DZ,027F4ZZ,027G04Z,027G0DZ,027G0ZZ,027G34Z,027G3DZ,027G3ZZ,027G44Z,027G4DZ,027G4ZZ,027H04Z,027H0DZ,027H0ZZ,027H34Z,027H3DZ,027H3ZZ,027H44Z,027H4DZ,027H4ZZ,027J04Z,027J0DZ,027J0ZZ,027J34Z,027J3DZ,027J3ZZ,027J44Z,027J4DZ,027J4ZZ,027K04Z,027K0DZ,027K0ZZ,	

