	02RH3KH,02RH3KZ,02RH47Z, ,02RH48Z,02RH4JZ,02RH4KZ, 02RJ07Z,02RJ08Z,02RJ0JZ,02 RJ0KZ,02RJ47Z,02RJ48Z,02RJ 4JZ,02RJ4KZ,02RK07Z,02RK0 8Z,02RK0JZ,02RK0KZ,02RK4 7Z,02RK48Z,02RK4JZ,02RK4 KZ,02RL07Z,02RL08Z,02RL0J Z,02RL0KZ,02RL47Z,02RL48 Z,02RL4JZ,02RL4KZ,02RM07 Z,02RM08Z,02RM0JZ,02RM0 KZ,02RM47Z,02RM48Z,02RM 4JZ,02RM4KZ,02RN07Z,02RN 08Z,02RN0JZ,02RN0KZ,02RN 47Z,02RN48Z,02RN4JZ,02RN4 KZ,02RP0JZ,02RQ07Z,02RQ0J Z,02RR07Z,02RR0JZ,02S00ZZ, 02S10ZZ,02SP0ZZ,02SW0ZZ,0 2SX0ZZ,02T50ZZ,02T53ZZ,02 T54ZZ,02T80ZZ,02T83ZZ,02T 84ZZ,02T90ZZ,02T93ZZ,02T9 4ZZ,02TD0ZZ,02TD3ZZ,02TD 4ZZ,	
	02TH0ZZ,02TH3ZZ,02TH4ZZ, 02TM0ZZ,02TM3ZZ,02TM4ZZ ,02TN0ZZ,02TN3ZZ,02TN4ZZ, 02U507Z,02U508Z,02U50JZ,02 U50KZ,02U537Z,02U538Z,02U 53JZ,02U53KZ,02U547Z,02U5 48Z,02U54JZ,02U54KZ,02U60 7Z,02U608Z,02U60JZ,02U60K Z,02U637Z,02U638Z,02U63JZ, 02U63KZ,02U647Z,02U648Z,0 2U64JZ,02U64KZ,02U707Z,02 U708Z,02U70JZ,02U70KZ,02U 737Z,02U738Z,02U73JZ,02U73 KZ,02U747Z,02U748Z,02U74J Z,02U74KZ,02U907Z,02U908Z ,02U90JZ,02U90KZ,02U937Z,0 2U938Z,02U93JZ,02U93KZ,02 U947Z,02U948Z,02U94JZ,02U 94KZ,02UA07Z,02UA08Z,02U A0JZ,02UA0KZ,02UA37Z,02U A38Z,02UA3JZ,02UA3KZ,02U A47Z,02UA48Z,02UA4JZ,02U A4KZ,02UD07Z,02UD08Z,02U D0JZ,02UD0KZ,02UD37Z,02U	

		D38Z,02UD3JZ,	
		02UD3KZ,02UD47Z,02UD48Z, 02UD4JZ,02UD4KZ,02UF07J,0 2UF07Z,02UF08J,02UF08Z,02 UF0JJ,02UF0JZ,02UF0KJ,02U F0KZ,02UF37J,02UF37Z,02UF 38J,02UF38Z,02UF3JJ,02UF3J Z,02UF3KJ,02UF3KZ,02UF47J ,02UF47Z,02UF48J,02UF48Z,0 2UF4JJ,02UF4JZ,02UF4KJ,02U F4KZ,02UG07E,02UG07Z,02U G08E,02UG08Z,02UG0JE,02U G0JZ,02UG0KE,02UG0KZ,02 UG37E,02UG37Z,02UG38E,02 UG38Z,02UG3JE,02UG3JZ,02 UG3KE,02UG3KZ,02UG47E,0 2UG47Z,02UG48E,02UG48Z,0 2UG4JE,02UG4JZ,02UG4KE,0 2UG4KZ,02UH07Z,02UH08Z,0 2UH0JZ,02UH0KZ,02UH37Z,0 2UH38Z,02UH3JZ,02UH3KZ,0 2UH47Z,02UH48Z,02UH4JZ,0 2UH4KZ,02UJ07G,02UJ07Z,02 UJ08G,02UJ08Z,02UJ0JG,02UJ 0JZ,02UJ0KG,02UJ0KZ,02UJ3 7G,02UJ37Z,02UJ38G,	

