		02UJ38Z,02UJ3JG,02UJ3JZ,02UJ3KG,02UJ3KZ,02UJ47G,02UJ47Z,02UJ48G,02UJ48Z,02UJ4JG,02UJ4JZ,02UJ4KG,02UJ4KZ,02UK07Z,02UK08Z,02UK0JZ,02UK0KZ,02UK37Z,02UK38Z,02UK3JZ,02UK3KZ,02UK47Z,02UK48Z,02UK4JZ,02UK4KZ,02UL07Z,02UL08Z,02UL0JZ,02UL0KZ,02UL37Z,02UL38Z,02UL3JZ,02UL3KZ,02UL47Z,02UL48Z,02UL4JZ,02UL4KZ,02UM07Z,02UM08Z,02UM0JZ,02UM0KZ,02UM37Z,02UM38Z,02UM3JZ,02UM3KZ,02UM47Z,02UM48Z,02UM4JZ,02UM4KZ,02UN07Z,02UN08Z,02UN0JZ,02UN0KZ,02UN37Z,02UN38Z,02UN3JZ,02UN3KZ,02UN47Z,02UN48Z,02UN4JZ,02UN4KZ,02VA0CZ,02VA0ZZ,02VA3CZ,02VA3ZZ,02VA4CZ,02VA4ZZ,02VR0ZT,02W50JZ,02W54JZ,02WA02Z,02WA03Z,02WA07Z,02WA08Z,02WA0CZ,02WA0DZ,02WA0JZ,02WA0KZ,02WA0MZ,02WA0QZ,02WA0RZ,02WA32Z,02WA33Z,02WA37Z,02WA38Z,02WA3CZ,	
		02WA3DZ,02WA3JZ,02WA3KZ,02WA3MZ,02WA3QZ,02WA3RZ,02WA42Z,02WA43Z,02WA47Z,02WA48Z,02WA4CZ,02WA4DZ,02WA4JZ,02WA4KZ,02WA4MZ,02WA4QZ,02WA4RZ,02WF07Z,02WF08Z,02WF0JZ,02WF0KZ,02WF47Z,02WF48Z,02WF4JZ,02WF4KZ,02WG07Z,02WG08Z,02WG0JZ,02WG0KZ,02WG47Z,02WG48Z,02WG4JZ,02WG4KZ,02WH07Z,02WH08Z,02WH0JZ,02WH0KZ,02WH47Z,02WH48Z,02WH4JZ,02WH4KZ,02WJ07Z,02WJ08Z,02WJ0JZ,02WJ0KZ,02WJ47Z,02WJ48Z,02WJ4JZ,02WJ4KZ,02WM0JZ,02WM4JZ,0	

		2YA0Z0,02YA0Z1,02YA0Z2,0 370046,037004Z,0370056,0370 05Z,0370066,037006Z,0370076, 037007Z,	
		0370346,037034Z,0370356,037 035Z,0370366,037036Z,037037 6,037037Z,0370446,037044Z,03 70456,037045Z,0370466,03704 6Z,0370476,037047Z,0371046,0 37104Z,0371056,037105Z,0371 066,037106Z,0371076,037107Z, 0371346,037134Z,0371356,037 135Z,0371366,037136Z,037137 6,037137Z,0371446,037144Z,03 71456,037145Z,0371466,03714 6Z,0371476,037147Z,0372046,0 37204Z,0372056,037205Z,0372 066,037206Z,0372076,037207Z, 0372346,037234Z,0372356,037 235Z,0372366,037236Z,037237 6,037237Z,0372446,037244Z,03 72456,037245Z,0372466,03724 6Z,0372476,037247Z,0373046,0 37304Z,	
		0373056,037305Z,0373066,037 306Z,0373076,037307Z,037334 6,037334Z,0373356,037335Z,03 73366,037336Z,0373376,03733 7Z,0373446,037344Z,0373456,0 37345Z,0373466,037346Z,0373 476,037347Z,0374046,037404Z, 0374056,037405Z,0374066,037 406Z,0374076,037407Z,037434 6,037434Z,0374356,037435Z,03 74366,037436Z,0374376,03743 7Z,0374446,037444Z,0374456,0 37445Z,0374466,037446Z,0374 476,037447Z,0375046,037504Z, 0375056,037505Z,0375066,037 506Z,0375076,037507Z,037534	

		6,037534Z,0375356,037535Z,0375366,037536Z,0375376,037537Z,0375446,037544Z,0375456,037545Z,0375466,	

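### The ICD procedure lists for the valvular AF exclusion do not match the valve repairs named in section 9.2, so many valve-repair codes exclude for 3 months instead of 12

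*Combined protocol and SAP*

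**What the plan says.** Section 9.2 (Setting, Subject Exclusion) uses two look-back windows. Cardiac surgery, pericarditis and myocarditis are treated as transient causes of AF and exclude only if found "3 months prior to index date in pre-period". Valvular AF excludes over the whole pre-period, which the same section sets at 12 months.

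The valvular list in section 9.2 names repairs as well as replacements. Examples are "Valvuloplasty, mitral valve, with cardiopulmonary bypass; with prosthetic ring", "Valvuloplasty, tricuspid valve; with ring insertion" and "Atrioventricular valve repair". Aortic valvuloplasty is also named.

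Appendix B, Table 3 turns these criteria into codes:

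- **Valvular block.** ICD procedure codes are given for open valvuloplasty (ICD-9 35.1x), valve replacement (35.2x) and closed valvotomy (35.0x), with ICD-10 equivalents. The mitral and tricuspid ring-repair rows hold a CPT code (33426, 33464), and their ICD columns are empty.
- **Cardiac Surgery row.** The ICD-9 entry is "00.5x, 35.xx, 36.xx, 37.xx". The long ICD-10 list beside it includes valve codes such as "02UJ38Z,02UJ3JG,02UJ3JZ,02UJ3KG,02UJ3KZ,02UJ47G", "02UG0KE,02UG0KZ" and "027G34Z,027G3DZ,027G3ZZ".

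In Appendix B, Table 2, the atrioventricular valve repair row carries V43.3 and Z95.2. These are the codes of the row directly above it, for a valve replaced by a mechanical device or prosthesis.

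**The concern.** The window that applies to a procedure depends on which block holds its code. If a repair named in section 9.2 as a whole-period exclusion has its ICD procedure code only under Cardiac Surgery, that code excludes for 3 months. The same operation found through a CPT code excludes for 12. Membership of the cohort then depends partly on which type of claim was captured.

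Non-valvular AF defines the study population, so the code lists ought to carry out the stated criterion. Any patient missed through this gap is one whom section 9.2 says should be out.

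**Working it through.** **1. The gap between the windows.** The valvular look-back is 12 months and the cardiac surgery look-back is 3 months. The exposed interval is 12 − 3 = 9 months: procedures more than 3 and up to 12 months before index.

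**2. Comparison of the two printed ICD-10 lists.** The valvular block of Table 3 holds 87 distinct ICD-10 procedure codes. These were set against the Cardiac Surgery codes whose fourth character is F, G, H or J, the letters that the plan's own valve rows use.

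| Family | In Cardiac Surgery | Also in valvular block | Only in Cardiac Surgery |
|---|---|---|---|
| 02U | 84 | 0 | 84 |
| 027 | 36 | 12 | 24 |
| 02Q | 21 | 4 | 17 |
| 02N | 12 | 12 | 0 |

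The totals follow from the pattern of the codes:

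- 02U: 24 codes each for F, G and J, and 12 for H, so 3 × 24 + 12 = 84.
- 027: 4 valves × 3 fifth characters × 3 endings = 36. The 12 with fifth character 0 are in both lists.
- 02Q: 6 + 6 + 3 + 6 = 21. Only the four ending in 0ZZ are in both lists.

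Codes with the 3-month window only: 84 + 24 + 17 = 125. The letter H accounts for 12 + 6 + 2 = 20 of them, which leaves 125 − 20 = 105 on F, G and J. The 02W valve codes (4 × 8 = 32) are also found only under Cardiac Surgery, as are 12 codes each in 024 and 025.

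**3. Near-identical codes with different windows.** 027F04Z is in the valvular block and 027F34Z is not. 02QF0ZZ is in the valvular block and 02QF0ZJ is not. This does not look like a rule that leaves fifth characters 3 and 4 to the short window, because the valvular block includes such codes for 02N and 02R.

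**4. ICD-9.** The valvular block has 35.0x, 35.1x and 35.2x. The rest of 35.xx is covered only by the Cardiac Surgery range.

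**5. The repair row in Table 2.** V43.3 and Z95.2 are already used one row higher for replaced valves. The atrioventricular valve repair row therefore adds no patient and identifies no repair.

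**6. What a missed patient needs.** All of these must hold: the procedure fell in the 9-month interval; no valvular CPT code in Table 3 was claimed; no valvular ICD procedure code in Table 3 was claimed; and no valvular diagnosis in Table 2 was claimed in the pre-period. The documents give no figure for any of these, so no patient count can be derived.

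**The case against.** The strongest reply is that other routes already exclude most of these patients for the full 12 months.

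- **CPT codes.** The valvular block lists 33425-33427 (mitral valvuloplasty, including ring repair and reconstruction), 33463-33464 (tricuspid, without and with ring) and 33400-33403. Section 9.4 says that CPT codes are among the data recorded for procedures in direct and purchased care.
- **Diagnoses.** Table 2 excludes over the whole pre-period on many valve codes, among them I05, I06, I07 and I08 entries, I34.0, I34.2, I35.0 and Z95.2-Z95.4.
- **Scope.** Section 9.2 names no percutaneous repair as such. For the pulmonary valve specifically it names only replacement and implantation. Some of the 125 codes may therefore not have been meant for the valvular block.
- **Code meaning.** The documents do not define 02U, or fifth characters 3 and 4. They also do not say whether an ICD-9 ring repair falls in 35.1x, which has the full window, or elsewhere in 35.xx.

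All of this stands, and it limits the point. A reader might infer that valve repair is coded only as cardiac surgery, that valvular AF patients therefore enter the cohort in material numbers, or that the comparison is biased. The documents support none of these. The first is false for CPT. The second needs a count of patients missed by every route, which is not given. The third needs a difference between arms, which nothing in the plan shows.

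The reply does not explain the mismatch itself. The plan lists ICD procedure codes for the valvular exclusion and so intends to use them, and nothing in section 9.2 or Appendix B gives a reason for one repair to have two look-backs.

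**Conclusion.** The point holds as an inconsistency between section 9.2 and its code lists. For the 02U, 027 and 02Q families, 125 valve codes (105 without the letter H) carry the 3-month window only. ICD-9 35.xx outside 35.0x-35.2x is treated in the same way, and the atrioventricular valve repair row does no work. A patient with a repair in the exposed 9 months can stay in the non-valvular cohort if no other listed valvular code was claimed.

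The code counts measure the mismatch in the lists and say nothing about how many patients are affected. That number is unknown from the documents and probably small, given the CPT and diagnosis routes. No shift in any treatment comparison is shown.

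Two assumptions are needed. One is that 02U, and the 027 and 02Q codes outside the valvular block, include the repairs that section 9.2 names; this comes from the code system. The other is that F, G, H and J stand for the aortic, mitral, pulmonary and tricuspid valves, which agrees with the order of valves and codes in the plan's replacement row.

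**What to change.** Before programming, reconcile the two blocks of Appendix B, Table 3:

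- Put ICD procedure codes for the repairs named in section 9.2 into the valvular block with the whole pre-period look-back. These are the 02U, 027 and 02Q codes on the aortic, mitral and tricuspid valves, and the matching valve-repair codes within ICD-9 35.xx, checked against the code books.
- In Table 2, replace the duplicated V43.3/Z95.2 in the atrioventricular valve repair row with codes that identify a repair.
- State whether pulmonary-valve codes and the 02W valve codes are meant to be included.

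A count, by arm, of patients removed only by the moved codes would show whether the change mattered. The work is a code-list edit, and the downside is that a few more patients are excluded.
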